## 5. Subject Disposition

## 5.1. Study Population

The number of subjects who were randomized and the number and percentage of subjects within each analysis population (ITT, safety, and PP) will be summarized for each treatment group for all randomized subjects. Vehicle Gel subjects will be separated into QD and BID groups. All percentages will be calculated based on the number of randomized subjects. A by subject list indicating subject's inclusion in each analysis population and reason(s) that subject is excluded from an analysis population will be presented.

### 5.2. Disposition

The counts and percentages of subjects who completed or discontinued from the study will be presented based on the number of subjects in each treatment group and overall for all randomized subjects. Vehicle Gel subjects will be separated into QD and BID groups. The reasons for study discontinuation will also be summarized. All percentages will be based on the number of subjects randomized. Subject disposition data will be listed as well.

### 5.3. Protocol Deviations

Protocol deviations will be tracked by the clinical team on an on-going basis. Specific criteria for what constitutes a significant protocol deviation will be documented in the Significant Protocol Deviations Rules document as noted above in section 4.3.3. Subjects with significant protocol deviations and protocol deviations which result in exclusion from the PP population will be tabulated for each treatment group and listed by subject for all randomized subjects. Vehicle Gel subjects will be separated into QD and BID groups. All percentages will be based on the number of subjects randomized.

#### 6. Demographics and Baseline Characteristics

#### 6.1. Demographics

Subject demographic and baseline characteristics will be summarized by treatment group and listed by subject for the ITT population. For continuous variables (e.g., age), mean, median, standard deviation, minimum and maximum will be presented. Categorical variables (e.g., ethnicity, race, smoking history, wart location at baseline [EGW only, PAW only, EGW and PAW]) will be summarized with frequency count and percentage by treatment group. Vehicle Gel subjects will be separated into QD and BID groups.

## 6.2. Medical History

Medical history will be collected in the Electronic Case Report Form (eCRF) at the screening and baseline visits and verbatim terms will be coded classified on the basis of Medical Dictionary for Regulatory Activities (MedDRA) terminology, which will be updated whenever possible throughout the life of the study. Medical history will be summarized by the number and percentage of subjects with any medical history reported by coded system organ class, preferred term, and treatment group for the ITT population. Vehicle Gel subjects will be separated into QD and BID groups. A subject listing will also be included with start date and end date or ongoing status.

### 6.3. Inclusion and Exclusion Criteria

Inclusion and exclusion criteria deviations noted in the eCRF will be presented for the set of randomized subjects in a data listing.

## 7. Treatments and Medications

### 7.1. Concomitant Medications

Any medicinal product, prescribed or over-the-counter (OTC), including herbal products, vitamins, and minerals is considered a concomitant medication. Any medications used during the study will be coded with the World Health Organization Drug Dictionary (WHODD), which will be updated whenever available throughout the life of the study.

Concomitant medication use will be recorded in the eCRF beginning on baseline after the first dose of study medication until the final visit (Week 12/ET visit). Any changes in concomitant medications will also be recorded in the subject's eCRF.

Summary of concomitant medications by treatment group and preferred term will be provided. All concomitant medications will be presented in data listings. Concomitant medications will be summarized for the safety population.

## 7.2. Study Treatments

Approximately 250 mg of NVN1000 Gel or Vehicle Gel will be mixed with an equal volume of hydrogel at each application. The mixed gel will be applied to the surface of all external genital and perianal warts identified by the investigator and to approximately 1 cm of surrounding normal skin for a period of up to 84 days. The test product and the hydrogel will be dispensed from separate 15 g aluminum tubes and stored by the subject at room temperature. The NVN1000 Gel and Vehicle Gel will be opaque and the hydrogel will be clear. The product should be mixed for 5-10 seconds until thoroughly combined with a uniform opaque appearance then applied.

## 7.2.1. Exposure and Compliance

Duration of exposure will be calculated in days as date of last dose of study medication– date of first dose of study medication+ 1. Percent compliance will be calculated as the number of total doses received divided by the number of planned doses times 100. The number of planned doses will be calculated as follows:

2 times the duration (days) of exposure - 1 for cohorts dosing twice daily,

and

1 time the duration (days) of exposure for cohorts dosing once daily,

The number of doses received will be calculated as the number of planned doses minus the total number of missed doses as indicated in the subject diaries. Descriptive statistics including the number of subjects, mean, standard deviation, median, minimum, and maximum for duration of study exposure and percent compliance will be provided by treatment group using the safety population. Vehicle Gel subjects will be separated into QD and BID groups for both exposure and compliance summaries. Compliance and treatment duration will also be listed by subject.

In addition, number of missed doses for each subject based on subject diaries will be summarized in a frequency table and listed by subject. Doses missed specifically for tolerability reasons will likewise be summarized in a frequency table and listed by subject.

For subjects who experience complete clearance, the number of missed doses and compliance will only be calculated up to and including the date of the first visit where the subject had a total wart count of 0. Any subsequent dosing due to recurrent warts will not be considered for analysis of missed doses or compliance.

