## 4.3.3. Per-Protocol Population

The PP population will include subjects with no noteworthy study protocol deviations (i.e., any subject or investigator activity that could have possibly interfered with the therapeutic administration of the treatment or the precise evaluation of treatment efficacy) prior to initial clearance of baseline warts, or Week 12/early termination if the subject does not achieve complete clearance at any time during the study. The PP population will include subjects in the safety population who do not meet any of the following criteria:

- Violated inclusion/exclusion criteria which have a potential impact on efficacy
- Have taken any concomitant medications likely to impact efficacy
- Have missed more than one interim study visit that they would have been eligible to attend as their EGW/PAW had not completely resolved
- Have not been compliant with the dosing regimen (i.e., subjects must apply 80-120% of the expected applications of study medication during participation in the study)

All significant protocol deviations will be documented in the Significant Protocol Deviations Rules document. Each significant deviation will be assigned a rule number and indication (yes/no) if the deviation will result in subject exclusion from the PP population. Prior to breaking the blind, other additional criteria may be added to the list to accommodate for unforeseen events that occurred during the conduct of the trial that result in noteworthy study protocol deviations. A by subject listing will be presented including the reason subjects are not included in any analysis population.

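### SAP 7.2.1, the only compliance formula given, does not yield the 80-120% quantity that SAP 4.3.3 asks for, and it counts off-drug time in restarters' exposure

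*SAP*

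**What the plan says.** **The PP rule.** SAP 4.3.3 removes subjects who did not comply with dosing, explained as "subjects must apply 80-120% of the expected applications of study medication during participation in the study". Protocol 7.2.3 sets the same band. Neither section gives a calculation or refers to SAP 7.2.1. SAP 4.3.3 adds: "All significant protocol deviations will be documented in the Significant Protocol Deviations Rules document". That document, which also flags which deviations lead to PP exclusion, is not part of the protocol or SAP.

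**The formula.** SAP 7.2.1 defines duration of exposure as last dose date minus first dose date plus 1. Planned doses are "1 time the duration (days) of exposure for cohorts dosing once daily", and twice the duration minus 1 for twice-daily cohorts. Doses received are "calculated as the number of planned doses minus the total number of missed doses as indicated in the subject diaries". Compliance is received over planned, times 100.

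**Cleared subjects and restarters.** After complete clearance, the missed-dose count and the compliance percentage are both cut short: each "will only be calculated up to and including the date of the first visit where the subject had a total wart count of 0". SAP 7.2.1 continues: "Any subsequent dosing due to recurrent warts will not be considered for analysis of missed doses or compliance". It states no such cut-off for duration of exposure. SAP 4 sets a restarter's last dose at the end of the second treatment interval.

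**Where the results go.** SAP 8.1.1 repeats the primary analysis in the PP population, and SAP 8.2 runs the secondary analyses in both ITT and PP. Interim Table 14.3-1 (SAP 10, Table 2) covers exposure and missed doses together.

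**The concern.** The rule and the formula appear to measure different things. The rule asks what share of expected applications was made over the time in the study, and it allows for over-use. The formula counts planned doses only between first and last dose and has no term for extra applications. If it is used for the PP rule, an over-user passes. An uncleared subject who stops early but keeps attending gets a score that depends on how the diary was filled in, not on the share of expected doses applied.

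A second mismatch affects the exposure tables. For restarters, exposure and missed doses run over different periods but appear in one table. That table is among the interim outputs meant to help plan future trials.

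**Working it through.** Notation: D = duration of exposure in days, P = planned doses, M = diary-missed doses. From SAP 7.2.1, P = D once daily (QD) and P = 2D - 1 twice daily (BID), with compliance = 100 × (P - M)/P. Planned treatment is 84 days (SAP 3.1), so full-course P is 84 QD and 2 × 84 - 1 = 167 BID. The plan states no compliance result to reproduce.

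**1. Upper limit.** M cannot be below 0, so (P - M)/P is at most 1 and compliance at most 100%. Breaching 120% over 84 days takes more than 1.2 × 84 = 100.8 QD applications or 1.2 × 167 = 200.4 BID applications. A subject making 101 QD (101/84 = 120.2%) or 201 BID (201/167 = 120.4%) with none missed scores 100%.

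**2. Lower limit for an uncleared subject who stops but stays.** Assume no missed dose before stopping and attendance to Day 84. SAP 7.2.1 does not say whether diary-missed doses after the last dose count, so both readings are shown.

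| Stop day | Regimen | P | 7.2.1, later days not logged as missed | 7.2.1, later days logged as missed | Share of 84-day expected |
|---|---|---|---|---|---|
| 14 | QD | 14 | 100% | (14 - 70)/14 = -400% | 14/84 = 16.7% |
| 14 | BID | 27 | 100% | (27 - 140)/27 = -418.5% | 27/167 = 16.2% |
| 28 | QD | 28 | 100% | (28 - 56)/28 = -100% | 28/84 = 33.3% |
| 56 | QD | 56 | 100% | (56 - 28)/56 = 50% | 56/84 = 66.7% |
| 67 | QD | 67 | 100% | (67 - 17)/67 = 74.6% | 67/84 = 79.8% |
| 68 | QD | 68 | 100% | (68 - 16)/68 = 76.5% | 68/84 = 81.0% |

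Neither reading returns the quantity in the rule. The first passes every such subject. The second gives impossible values but puts most of them on the correct side of 80%.

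The floor does work for doses missed between first and last dose over a full course: 17 missed QD gives 67/84 = 79.8%, and 34 missed BID gives 133/167 = 79.6%.

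**3. Restarters.** Take a subject on drug Days 1-14, cleared, then back on drug Days 57-84. Reported duration is 84 - 1 + 1 = 84 days. Time on drug is 14 + (84 - 57 + 1) = 14 + 28 = 42 days. Missed doses are counted only to the first visit with no warts, so Table 14.3-1 would set an 84-day exposure beside misses from the first course alone.

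Planned doses are also defined from duration, and no shortened duration is given. If a programmer cut the misses at Day 28 but kept D = 84, 7 missed QD doses would score (84 - 7)/84 = 91.7% instead of (28 - 7)/28 = 75.0%. The natural reading of SAP 7.2.1 cuts both, but the text should say so.

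**The case against.** The strongest objections concern the second problem and the link to PP.

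- **Stoppers kept in PP.** A reader might infer that subjects who stop and stay will be scored 100% and retained. The documents do not support that. SAP 7.2.1 does not limit missed doses to those before the last dose, and sites review diaries for missed applications (Protocol 4.1.3 to 4.1.6), so later days may well be logged. Most such subjects would then fall below 80%, as the rule intends.
- **How many such subjects.** The criteria in Protocol 6.7 remove subjects from the study, not only from drug, and Protocol 4.1.7 places the early-termination evaluations at that time. Unblinded subjects stop drug and are encouraged to stay, but only until the event resolves or stabilises (SAP 4.2). SAP 9.1.5 identifies drug withdrawal and study discontinuation separately, which does not show continued attendance. The planned table in SAP 7.2.1 ("Doses missed specifically for tolerability reasons will likewise be summarized in a frequency table and listed by subject") shows that such misses are expected, not that subjects stop and stay.
- **Use of 7.2.1 for PP.** SAP 4.3.3 does not cite it. The Rules document may hold another calculation, and the general deviation clause in 4.3.3 could exclude stoppers or over-users. Returned-drug accountability might reveal over-use.
- **Cleared subjects.** A reader might infer a further conflict because the deviation period in SAP 4.3.3 is "prior to initial clearance of baseline warts, or Week 12/early termination if the subject does not achieve complete clearance", while 7.2.1 runs to a total wart count of 0. That does not hold: the 80-120% criterion speaks of participation in the study, and new warts are still treated (Protocol 4.2.1), so those doses belong in the count.
- **Restarters.** The duration rule is stated openly and, on the natural reading, does not change their compliance or PP status.

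These points limit the size of the problem. They do not rescue the 120% limit under 7.2.1, the missing end for diary misses, or the off-drug days in exposure.

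**Conclusion.** The point holds as a minor one. Two parts follow directly from the stated rules: compliance under 7.2.1 is capped at 100%, so the 120% limit can exclude no one if that formula is used, and restarters' exposure counts the off-drug gap (84 against 42 days in the example). The third part is conditional: an uncleared QD subject who stops on Day 14 and attends to Day 84 scores 100% or -400% against a true 16.7%, depending on diary practice that the SAP leaves open.

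The effect on PP membership, and so on the PP analyses, assumes that 7.2.1 is the calculation used and that the Rules document contains no other. The exposure and compliance tables are affected regardless. The number of subjects involved cannot be derived from the documents and is probably small. The ITT primary analysis does not use compliance and is unaffected.

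**What to change.** In SAP 7.2.1, calculate planned, missed and received doses over one common window:

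- **Uncleared subjects:** from first dose to the earlier of the Week 12 visit or the recorded date of study discontinuation. Count every unapplied dose in that window as missed.
- **Cleared subjects:** keep the present cut-off at the first visit with a total wart count of 0, and say that it applies to planned as well as missed doses.
- **Link:** state in SAP 4.3.3 that the 80-120% rule uses this calculation.
- **Over-use:** count extra applications if the diaries record them, which the documents do not show. Otherwise drop the 120% limit.
- **Exposure:** report restarters' exposure as the sum of the on-treatment intervals.

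The discontinuation date is preferred to a later early-termination visit date because the wait for that visit would count against early terminators. A subject who stopped on Day 14 and was seen on Day 18 would score 14/18 = 77.8% QD or 27/35 = 77.1% BID with no dose missed while on treatment. The team should confirm that this date is captured separately from the visit date.

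The cost is SAP wording and minor reprogramming before unblinding. The PP population may become slightly smaller.

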#### 8. Efficacy Analysis

Efficacy data is collected at each study visit. Wart count data including derived primary and secondary endpoint data such as complete clearance, time to complete clearance, time to recurrence, etc. will be presented in listings by subject. Subjects may receive more than one course of treatment if they experience complete clearing and subsequent recurrence of warts. Assessment of time to clearing, time to recurrence, and clearing at or before Week 12 will be assessed based on the initial treatment course (i.e., first instance of clearing/recurrence only.) For efficacy assessments by visit (i.e., at Weeks 2, 4, 8 and 12), data will be summarized without regard to treatment course. (e.g., assessments at Week 8 may include data for subjects still on their initial treatment course as they have not yet achieved clearance, subjects off treatment as they have previously cleared but not yet experienced a recurrence, and subjects on a second course of treatment after prior clearance and recurrence.)

Wart count data including derived primary and secondary endpoint data such as complete clearance, time to complete clearance, time to recurrence, etc. will be presented in data listings by subject.

#### 8.1. Primary Efficacy Endpoint

## 8.1.1. Proportion of Subjects with Complete Clearance of Baseline EGW/PAW at or Before Week 12

The primary efficacy endpoint is the proportion of subjects with complete clearance of baseline EGW/PAW at or before Week 12.

The number and proportion of subjects with complete clearance of baseline warts will be summarized by treatment group and each active dose group will be compared to vehicle using pairwise Pearson's chi-square tests. The Mantel-Haenszel odds ratios and corresponding 95% confidence interval (CI) will be presented. The Vehicle Gel arm will be separated into once-daily (QD) and twice-daily (BID) groups and compared pairwise to the corresponding active treatments. The three once-daily active treatment groups (8%, 16%, and 24%) will be compared to the Vehicle Gel QD group and the NVN1000 8% BID group will be compared to the Vehicle Gel BID group. The pairwise comparisons will be computed without concern for controlling for multiplicity. The primary analysis will be performed for the ITT population.

Percentages will be calculated based on the number of subjects in the ITT analysis population. Subjects who have clearance of baseline warts at or before the Week 12 visit will be counted as cleared for the analysis. Subjects who do not have a documented clearance by the end of study, including subjects with missing data at the Week 12 or other assessments, will be considered not cleared for the analysis.

The primary analysis will be repeated for the PP population. Subgroup analysis for gender and wart location (EGW/PAW) will also be performed for the ITT population. The subgroup summaries will be descriptive only with no statistical hypothesis testing performed.

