# 3.7.2 INCLUSION CRITERIA

Each subject must fulfill all of the following inclusion criteria to participate in the study:

- 1. Have a signed written informed consent form (ICF);
- 2. Be male or female, 18 to 50 years of age, inclusive and in good general health;
- 3. Have a minimum of two but not more than 20 EGW/PAW with a maximum total wart surface area less than the area of the subject's palm (approximately 1% BSA);

- 4. If currently receiving treatment for EGW/PAW at the time of screening, be willing to discontinue treatment for 28 days prior to randomization and during the study;
- 5. Women of childbearing potential (WOCBP) must have a negative urine pregnancy test (UPT) prior to randomization;
- 6. WOCBP must agree to use an effective method of birth control during the course of the study and for 30 days after their final study visit;
- 7. Be willing and able to follow study instructions and likely to complete all study requirements.

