# 7. STATISTICAL ANALYSIS

### 7.1 GENERAL CONSIDERATIONS

All statistical processing will be performed using SAS® version 9.2 or higher unless otherwise stated. Statistical significance will be based on two-tailed tests of the null hypothesis resulting in p-values of ≤0.05 unless stated otherwise. Inferential testing will compare each active treatment group to the Vehicle treatment group. Comparisons will not be performed between active treatments. Efficacy analyses will be performed for the intent-to-treat (ITT) and per-protocol (PP) populations. Safety analyses will be performed using the safety population.

An interim analysis may be conducted upon completion of Cohorts 1 and 2. A detailed description of the statistical methodology and data reporting for the interim and complete analysis for this study will be provided in the Statistical Analysis Plan (SAP). The SAP will be finalized before the database is locked and released to Novan. Any deviations from the SAP will be justified in the clinical study report.

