#### 3. Investigational Plan

#### 3.1. Overall Study Design and Plan

Subjects will dose for up to 12 weeks (84 days) with NVN1000 Gel or Vehicle Gel coadministered with an equal volume of a carboxymethyl cellulose hydrogel. Subjects will be randomized 3:1 to active:vehicle in 4 dose cohorts initiated at NVN1000 8% Gel. The safety/tolerability of each cohort will be assessed by an independent data safety monitoring board (DSMB) after the first 12 subjects of each cohort complete 2 weeks of dosing.

Figure 3–1 depicts the overall study design for this 12 week, variable dose, randomized, double blind study in subjects with EGW/PAW dosed with NVN1000 Gel or Vehicle Gel. Subjects receiving current treatment for EGW/PAW may enter a wash out period after screening of up to 35 days prior to randomization.

Subjects who are found to be cleared of all warts at a visit will discontinue treatment at that time. If warts recur at a subsequent visit prior to end of treatment, subjects will be dispensed a new kit of the same treatment they previously received.

		Vehicle Gel	to match cohort	dosing	
			el 8% twice dai	ly (Cohort 1)	
	Randomization: 3:1	- NVN1000 C	el 8% once dail	y (Cohort 2)	
	active.venicle	- NVN1000 C	el 16% once dai	ily (Cohort 3)	
		- NVN1000 C	el 24% once dai	ily (Cohort 4)	
Visits		T T' '. 1			
Screening	Baseline	Visit I	Visit 2	Visit 3	Visit 4/ET
Day -35 to Day -1	Day 0	Day 14	Day 28	Day 56	Day 84
	Study Week	2	4	8	12

Figure 3–1: Study Diagram

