## 4.1. Sample Size

This study is not powered to detect a statistical difference in efficacy between treatment groups. Approximately 120 subjects will be randomized into the study in a 3:1 ratio (active:vehicle) at approximately 15 sites in North America. The number of subjects enrolled in any dosing cohort is dependent on the recommendations of the DSMB and enrollment rates. The main objective of this study is to evaluate the tolerability, safety, and efficacy of topical NVN1000 Gel.

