#### 4.2. Randomization, Stratification, and Blinding

Subjects will be randomized to variable doses of NVN1000 or Vehicle Gel in a 3:1 ratio (active:vehicle) through utilization of the interactive voice response system/interactive web response system (IVRS/IWRS). The evaluator, Investigator, and subject will be blinded to the subject's treatment. NVN1000 Gel and Vehicle Gel are similar in appearance and cannot be differentiated.

In the event that a subject should experience an AE for which it is medically required to break the blind in order to determine appropriate treatment, unblinding can be achieved by using the IVRS/IWRS administrator. A study subject for whom the blind is broken

will discontinue study product and will be scheduled for a follow- up safety visit and be encouraged to stay in the study until the AE is resolved or stabilized. Although not required, the Investigator should contact PPD medical monitor prior to breaking the blind.

Randomization treatment assignment and actual treatment received will be presented in a by subject listing.

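### The primary clearance comparison makes no use of the recorded baseline wart count; for the once-daily comparisons, prespecify a count-stratified analysis alongside the crude one

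*SAP*

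**What the plan says.** SAP 8.1.1 specifies for the primary endpoint that "each active dose group will be compared to vehicle using pairwise Pearson's chi-square tests", and then: "The Mantel-Haenszel odds ratios and corresponding 95% confidence interval (CI) will be presented". It names no stratum and no covariate. The three once-daily (QD) active groups are each compared with the QD vehicle group, and the twice-daily (BID) group with BID vehicle. Significance is judged at two-sided 0.05 (Protocol 7.1), with no multiplicity control.

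On allocation, SAP 4.2 says "Subjects will be randomized to variable doses of NVN1000 or Vehicle Gel in a 3:1 ratio", and Protocol 8.3 places this within each cohort. Neither section states stratification by wart number.

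On the baseline count, Protocol 3.7.2 requires subjects to "Have a minimum of two but not more than 20 EGW/PAW with a maximum total wart surface area" below a stated limit. Protocol 4.1.2 and 4.2.1 have the count recorded at Baseline. SAP section 4 defines complete clearance as zero warts.

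Other uses of baseline data are limited. SAP 8.1.1 states: "Subgroup analysis for gender and wart location (EGW/PAW) will also be performed for the ITT population", and these summaries are descriptive only. SAP 6.1 gives wart location, but not wart number, among its examples of baseline characteristics. SAP 8.2.7 does summarise wart counts at baseline by group.

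**The concern.** The endpoint is all-or-nothing, so a subject with 2 warts plausibly has an easier target than one with 20. Allocation is not balanced on count, the arms are small, and the primary analysis has no means of accounting for an imbalance. A reader could see from the SAP 8.2.7 summaries that one arm started with fewer warts, but no planned analysis would say how much of the clearance difference that explains. An adjustment chosen after unblinding would carry little weight.

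At stake is how a single result is read. SAP section 10 has the primary clearance table, with nominal p-values, produced at the interim to help plan later trials. A few points of spurious difference could carry into that planning.

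**Working it through.** **Arm sizes.** The documents give about 120 subjects and "Subjects will be randomized 3:1 to active:vehicle in 4 dose cohorts initiated at NVN1000 8% Gel". They give no power calculation to reproduce, and SAP 4.1 leaves cohort size to the DSMB and enrolment. Assuming equal cohorts: 120/4 = 30 each; active 30 × 3/4 = 22.5; vehicle 30 × 1/4 = 7.5; QD vehicle from Cohorts 2 to 4, 3 × 7.5 = 22.5. So QD is about 22 against 22, and BID about 22 against 7 or 8.

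**The odds ratio.** The Mantel-Haenszel estimate is Σ(ad/n) / Σ(bc/n) over strata. With one stratum, n cancels and it is ad/bc, the crude odds ratio.

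**Assumptions, none of them in the documents.** Counts uniform on 2 to 20; 20% clearance overall; log-odds of clearance falling 0.15 or 0.25 per wart; no drug effect. These slopes imply clearance of about 44% at 2 warts and 5% at 20 (slope 0.15), or 59% and 2% (slope 0.25).

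**How often imbalance occurs.** The SD of a uniform count on 19 values is √((19² − 1)/12) = √30 = 5.48.
- QD: SD of the difference in means = 5.48 × √(1/22 + 1/22) = 1.65. A gap of 2 warts is 2/1.65 = 1.21 SD: 11% in one direction by the normal approximation, 11 to 12% by simulation.
- BID (22 against 8): 5.48 × √(1/22 + 1/8) = 2.26. The gap is 0.885 SD, 19% in one direction.

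**Size of the shift, given 2 or more fewer warts in the active arm.** The mean gap is SD × φ(z)/(1 − Φ(z)). Multiply it by the slope and by the average of p(1 − p) over the count range (0.145 at slope 0.15; 0.127 at slope 0.25).
- QD: 1.65 × 0.192/0.113 = 2.80 warts. Then 2.80 × 0.15 × 0.145 = 0.061 and 2.80 × 0.25 × 0.127 = 0.089. Simulation gives 6.0 and 8.7 points.
- BID: 2.26 × 0.270/0.188 = 3.25 warts. Then 3.25 × 0.15 × 0.145 = 0.071 and 3.25 × 0.25 × 0.127 = 0.103. Simulation gives 6.9 and 9.8 points.

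**Rejection under the null (simulation; stratified test uses three count bands).**

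| Comparison | Crude, all trials | Stratified, all trials | Crude, unlucky subset | Stratified, unlucky subset |
|---|---|---|---|---|
| QD | about 5% | about 5% | 7.0–7.5% (slope 0.15); 9.1–9.8% (slope 0.25) | 4.7–5.0% |
| BID, 22 vs 8 | 4.1–4.3% | 4.0–4.2% | about 3% | 3.0–3.4% |

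The QD ranges reflect rounding 22.5 to 22 or 23. With a skewed count distribution the false advantage is 5 to 8 points.

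The BID test does not over-reject because its vehicle arm is too small. With no clearances among 8 vehicle subjects and A among 22 active, chi-square = 30 × 8A / (22 × (30 − A)). This is 1680/506 = 3.32 at A = 7 and 1920/484 = 3.97 at A = 8, against a critical value of 3.84. Even then, 8 of 22 must clear.

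**Power, crude then stratified (assumed log-odds ratio 1.4).** QD: 45% to 48% (slope 0.15), 33% to 40% (slope 0.25), 56% to 55% if count is unrelated to clearance. BID: 25.2% to 24.5%, 18.0% to 19.8%, 32.7% to 29.1%.

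**The case against.** The strongest reply is that nothing is broken. Chance imbalance is already in the test's error rate: the crude test holds about 5% and the average shift is zero. The higher rejection rates belong to a selected, unlucky subset. This stands. A reader might infer that the planned test is invalid or has inflated error; neither the documents nor the calculation supports that.

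The shift is also a minority of the noise. Under the assumptions above its SD is 3.7 to 5.4 points against a total of 12.1, or (3.7/12.1)² = 9% to (5.4/12.1)² = 20% of the variance. Weaker assumed associations give 3 to 11%.

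A reader might expect the BID comparison, with its 7 or 8 vehicle subjects, to suffer most. Its estimate does shift, but its test is not inflated, and stratifying it is unattractive: with three bands, at least one stratum is uninformative in 65 to 84% of null trials.

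A reader might also want sex as a stratum. The documents give no link between sex and clearance, and a descriptive gender subgroup is already planned.

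Finally, the study is declared not powered for efficacy and its p-values are nominal, so no confirmatory decision hangs on this. That limits the weight of the point but does not remove it: the SAP still tests at 0.05, and the estimates will inform later trials. The baseline summaries and percent-change analyses show an imbalance but do not correct the primary comparison for it.

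**Conclusion.** The point holds as a cheap improvement, not as an error in the plan. The primary analysis is crude, its Mantel-Haenszel label has no stratum behind it, and a recorded, plausibly strong predictor is unused. In about 12% of QD comparisons, chance would favour the active arm by 2 or more warts. The result would then be a false advantage of about 6 to 9 points and a conditional rejection rate of roughly 7 to 9.5%, which stratification returns to about 5%. For BID the consequence is confined to the estimate.

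These sizes rest on equal cohorts, 20% clearance, the assumed count distribution and the assumed slopes. If count does not predict clearance, there is no shift. The calculation also treats imbalance as pure chance. QD vehicle comes from successive cohorts, so a drift in enrolled wart burden would add to it.

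**What to change.** In SAP 8.1.1, for the three QD comparisons, prespecify a Cochran-Mantel-Haenszel test and the matching Mantel-Haenszel odds ratio, stratified by baseline wart count. Use two or three bands fixed on blinded data. Report these alongside the crude Pearson test, and say in advance which is quoted first.

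For BID, keep the crude analysis and call its odds ratio crude. Any count-adjusted estimate there should be supportive only and use a sparse-data method such as Firth logistic regression.

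Add baseline wart count to the SAP 6.1 baseline table. Sex need not be a stratum.

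Cost: SAP wording, a little programming, and about 1 point of QD power if count is unrelated to clearance. No new data are needed.
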